10.5.5. Pharmacokinetic/Pharmacodynamic Statistical Analysis

Further details of the planned PK/PD correlation analysis will be provided in the SAP.

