15.2. Appendix 2– Schedule of Assessments (Part B)

Schedule of Assessments Part B	Screening Up to 28 Days	Screening 2 Prior to Day -1	Treatment Period		Post-Study (5 to 7 days post-final dose)
			Day -1	Day 1	
Informed Consent	X				
Demography	X				
Inclusion/Exclusion Criteria ^a	X				
Medical History	X				
Urine Drugs of Abuse and Breath Alcohol Screen	X		X		
SARS-CoV-2 Test	X		X		
Serology	X				
Study Residency					
Admission			X		
Discharge				12 hours postdose	
Non-Residential Visit	X				X
KLS-GABA/ KLS/Gabapentin/ Placebo Administration				X	
Safety Assessments					
Physical Examination	X				X
Vital Signs (HR, BP and oral temperature) ^b	X		X	Predose, 1, 2, 4, 8 and 12 hours postdose	X
12-Lead ECG ^c	X			Predose, 1, 4 and 12 hours postdose	X
Clinical Laboratory Evaluations	X		X		X
AE and Concomitant Medication Monitoring	X	X	X	Predose, 1, 2, 3, 4, 6, 8 and 12 hours postdose	X
Plasma Concentration Assessments					
Blood Sampling				Predose, pre-capsaicin and 2 hours post capsaicin	

Pharmacodynamic Assessments					
Intradermal Capsaicin Injection		X ^d	X ^e	X ^f	
Pain Measurement		X ^g	X ^h	X ^h	

Abbreviations: AE – adverse event; BP – blood pressure; ECG – electrocardiogram; GABA – Gabapentin; HR – heart rate; KLS - Ketoprofen Lysine Salt SARS-CoV-2 – severe acute respiratory syndrome coronavirus 2.

a A full check of inclusion/exclusion criteria will take place at screening. At all other days to which inclusion/exclusion criteria apply, only those particular inclusion/exclusion criteria will be checked

b Supine only.

c ECG assessments will be conducted within a ±30 minute time window.

d Additional screening visit at least 7 days prior to dosing to determine response to capsaicin and vehicle injections

e At a similar time of day to that anticipated on Day 1

f At estimated T_{max} for KLS alone or KLS-GABA from Part A

g Pain VAS, Flare, Hyperalgesia, Allodynia conducted pre-capsaicin injection and 15 minutes post injection.

h Pain VAS, Flare, Hyperalgesia, Allodynia conducted pre-capsaicin injection and 15, 30, 60, 90 and 120 minutes post injection

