1.1.4. Secondary Objectives (Part B)

The secondary objectives of the Part B are:

- To further investigate the safety, tolerability, and PK of single oral doses of KLS-GABA and KLS alone.
- To investigate the possible relationship between plasma levels of drug and efficacy in pain reduction.

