3. CONVENTIONS

All summary tables, figures and data listings will be produced using SAS software 9.4 or above.

Summaries will be performed by treatment group, separately for Part A (crossover design) and Part B (parallel design).

Descriptive statistics will be used for all variables, as appropriate. Continuous variables will be summarised by the number of observations, mean, standard deviation, median, minimum, and maximum. For log-transformed data, the geometric mean, coefficient of variation (CV), median, minimum and maximum will be presented. No hypothesis testing will be conducted.

Categorical variables will be summarised by frequency counts and percentages for each category.

For AE summaries, the n and % of subjects with event, as well as the number of events, will be shown.

For all Part A endpoints, the last observation before the first dose of corresponding study treatment will be considered the baseline measurement unless otherwise specified. However, if an evaluable assessment is only available after randomisation but before the first dose of randomised treatment then this assessment will be used as baseline. For Part A, baseline for each treatment period will be defined as last observation before the first dose of study treatment (Period 1 Day -1 and Period 2 Day-1).

For Part B safety and PK endpoints, the last observation before dosing will be considered the baseline measurement unless otherwise specified. However, if an evaluable assessment is only available after randomisation but before the first dose of randomised treatment then this assessment will be used as baseline.

For Part B PD endpoints, the day -1 observation at each post-Capsaicin injection timepoint will be considered the baseline measurement for each corresponding day 1 post-Capsaicin timepoint, i.e., the baseline for day 1 15 minutes post-Capsaicin injection will be the day-1 15 minutes post-Capsaicin injection value. If a day-1 PD value at the 30-minute, 60-minute or 90-minute post-Capsaicin timepoints is missing for a subject, linear interpolation will be used to compute the missing value. If a subject's 120-minute post-Capsaicin value is missing, last observation carried forwards (LOCF) will be used instead. If a subject's 15-minute post-Capsaicin value is missing, next observation carried backwards (NOCB) will be used.

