6.8.1. Descriptive PD analysis

Descriptive statistics will be calculated for absolute value and change from baseline (with baseline defined as the day -1 observation at each post-Capsaicin injection timepoint) for Scores (VAS or NRS) and Area measured (cm²) by visit and by treatment according to treatment period.

The list of PD parameters includes:

- area of hyperalgesia (Primary Endpoint);
- measurement of pain score;
- pain score of hyperalgesia;
- area of allodynia;

Statistical Analysis Plan

- pain score of allodynia;
- area of flare.

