6.8.4. Pharmacokinetic/Pharmacodynamic Statistical Analysis

The relationship between the PK parameters and PD parameters will be investigated by estimating the Pearson and Spearman correlation coefficients by treatment. This analysis will be conducted for Part B only based on PK population.

Statistical Analysis Plan

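### SAP 6.8.4 plans simple PK/PD correlations, states no adjustment for the Day -1 capsaicin response and does not say which form of the PD variable is used, so the estimate may be diluted

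*SAP*

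**What the plan says.** The Part B secondary objective served here is "To investigate the possible relationship between plasma levels of drug and efficacy in pain reduction" (SAP 1.1.4). Protocol 10.5.5 leaves the method to the SAP: "Further details of the planned PK/PD correlation analysis will be provided in the SAP".

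SAP 6.8.4 is two sentences long. The first gives the method: "The relationship between the PK parameters and PD parameters will be investigated by estimating the Pearson and Spearman correlation coefficients by treatment". The second gives the population: "This analysis will be conducted for Part B only based on PK population". No covariate, partial correlation, timepoint or form of the PD variable is named.

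The Day -1 response is available. Protocol Appendix 2, in a footnote attached to the pain measurements of both Day -1 and Day 1, has "Pain VAS, Flare, Hyperalgesia, Allodynia conducted pre-capsaicin injection and 15, 30, 60, 90 and 120 minutes post injection". SAP Section 3 then fixes how PD baselines are taken in Part B: "the day -1 observation at each post-Capsaicin injection timepoint will be considered the baseline measurement for each corresponding day 1 post-Capsaicin timepoint". The mixed models of SAP 6.8.3 include this baseline as a covariate.

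SAP 6.8.1 opens its list of six measures with "The list of PD parameters includes" and gives areas and scores by name. The same section also says "Descriptive statistics will be calculated for absolute value and change from baseline", so both forms exist for each measure. SAP 6.8.3 models the value and the change as separate dependent variables.

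**The concern.** Subjects differ in how strongly they react to the same capsaicin dose. A large area of hyperalgesia on Day 1 may reflect a strong responder rather than a low plasma level. If that variation stays in the PD variable, it adds spread unrelated to exposure and shrinks the correlation.

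Taking the change from Day -1 does not fully solve this. It subtracts the whole Day -1 value, including the part that does not carry over to Day 1, and so can put noise in as well as take responsiveness out.

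At stake is the reported estimate for a named secondary objective: a real exposure-response relation could look weaker than it is, and in the same direction in every arm. Because SAP 6.8.4 leaves the form open, the choice between absolute value and change could also be made after the data are seen.

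**Working it through.** **Plan's own figure.** There is none to reproduce. Protocol 10.2 reports no formal sample size calculation, and neither document gives a precision target for the correlation. The group size follows from the design: 128 subjects / 8 treatments = 16 per treatment.

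**Assumed inputs (not in the documents).**
- rho, the correlation of a subject's Day -1 and Day 1 responses at the same timepoint: range 0.3 to 0.7.
- r, the PK/PD correlation after adjustment for Day -1: 0.50 for illustration.
- Plasma level independent of the Day -1 response.
- Equal variances on the two days (needed for the change-score formula).

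**Formulas (Pearson).** Write Day 1 = rho × (Day -1) + sqrt(1 - rho²) × e in standardised units, where e correlates r with plasma level.
- Absolute Day 1 value: r × sqrt(1 - rho²).
- Change from Day -1: the change has variance 2(1 - rho), so the correlation is r × sqrt(1 - rho²) / sqrt(2(1 - rho)) = r × sqrt((1 + rho)/2).
- Partial correlation given Day -1: r.

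**Results at r = 0.50.**

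| rho | Absolute: factor, loss | Absolute: correlation | Change: factor, loss | Change: correlation | Partial |
|---|---|---|---|---|---|
| 0.3 | sqrt(0.91) = 0.954, 5% | 0.48 | sqrt(0.65) = 0.806, 19% | 0.40 | 0.50 |
| 0.5 | sqrt(0.75) = 0.866, 13% | 0.43 | sqrt(0.75) = 0.866, 13% | 0.43 | 0.50 |
| 0.7 | sqrt(0.51) = 0.714, 29% | 0.36 | sqrt(0.85) = 0.922, 8% | 0.46 | 0.50 |

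A simulation of 400,000 draws agreed: 0.477, 0.434 and 0.359 for the absolute value, and 0.403, 0.434 and 0.460 for the change.

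The two unadjusted forms cross at rho = 0.5. Below it the change score is the worse choice; above it the absolute value is.

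**Precision at n = 16 (Fisher z).** atanh(0.50) = 0.549.
- Simple correlation: half-width 1.96 / sqrt(16 - 3) = 0.544, so the 95% CI is tanh(0.006) to tanh(1.093), about 0.01 to 0.80.
- Partial correlation, with one degree of freedom fewer: half-width 1.96 / sqrt(16 - 4) = 0.566, so the interval is tanh(-0.017) to tanh(1.115), about -0.02 to 0.81.

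The cost of adjustment is therefore a barely wider interval, and sampling error exceeds the dilution at moderate rho.

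**The case against.** The strongest reply is that nothing in the documents says Day -1 is left out. A reader might infer that SAP 6.8.4 correlates raw Day 1 values, because SAP 6.8.1 lists the measures by name and SAP 6.8.3 names change separately. That is the literal reading, but it is not established. SAP Section 3 sets the Day -1 baseline for Part B PD endpoints generally, the SAP's primary endpoint is worded as a reduction, and so is the objective. A change-score correlation fits at least as well. This part of the objection stands, and the point is therefore conditional on the form used.

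A reader might also turn the dilution into lost power. On the raw reading with r = 0.50, rho = 0.7 and n = 16, the chance that a 95% CI excludes zero is 27%, against 48% with adjustment. Three doses pooled (n = 48, r = 0.4) would show a gap of 30 points. The documents do not support presenting the gain that way:
- SAP Section 3 rules out hypothesis testing.
- SAP 6.8.4 works by treatment, and pooled doses are defined only for the combined models of SAP 6.8.3.
- On the change-score reading at rho = 0.7 the gaps shrink to about 4 and 6 points.

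Nor is this the only PD output without baseline adjustment: SAP 6.8.1 also summarises absolute values, and the figures of SAP 6.8.2 state no adjustment.

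Finally, with 16 per arm, random error may swamp the dilution. That is true of any one arm. But random error has no preferred direction, whereas dilution pulls towards zero in every arm and for every measure, and the data that remove it are already collected.

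**Conclusion.** The point holds in a conditional form. SAP 6.8.4 states no adjustment for the Day -1 response and does not define the PD variable. Whichever form is used, a simple correlation understates the baseline-adjusted one: by 5% to 29% for the absolute value and by 19% to 8% for the change score as rho goes from 0.3 to 0.7. A partial correlation removes this at every rho.

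The figures rest on an assumed rho, on equal variances, and on plasma level being unrelated to the Day -1 response. They are derived for Pearson; for Spearman they are a guide only. The benefit is a less biased estimate in a descriptive secondary analysis. It is modest beside the sampling error at n = 16, but nearly free.

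**What to change.** In SAP 6.8.4, before unblinding:
- Make the main analysis partial Pearson and partial Spearman correlations, by treatment, between plasma concentration and the Day 1 PD value at a named post-capsaicin timepoint, adjusted for the same subject's Day -1 value at that timepoint, with 95% CIs.
- Name which Part B plasma sample is paired with which PD timepoint. Protocol 10.5.3.1 derives non-compartmental parameters for Part A only, and Part B has three samples (predose, before capsaicin and 2 hours after it), so the PK side needs defining too.
- Keep the unadjusted coefficients as a supplement, and say whether they use the absolute value or the change.

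The cost is a few lines of SAP text, a partial-correlation option in the program and one degree of freedom per correlation. No new data are needed.

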7. HANDLING OF MISSING OR INCOMPLETE DATA

Unrecorded values, other than PD baseline values, will be treated as missing. Efforts will be made to prevent this from occurring. For complete missing visits, the missing data will be treated as missing at random and will not be imputed in the statistical analysis except for partial dates.

As mentioned in Section 3, any missing PD baseline values at the 30-minute, 60-minute and 90-minute post-Capsaicin timepoints will be imputed using Linear Interpolation. Missing PD baseline values at the 15-minute and 120-minute post-Capsaicin timepoints will be imputed using NOCB and LOCF, respectively. If there are any missing PD baseline values, the imputed values will be clearly flagged in the listings. Separate summary statistics tables will be created for the PD data with non-imputed values and the PD data with imputed values.

7.1. Prior and Concomitant Medication Dates

Partial dates for any prior and concomitant medications recorded in the eCRF will be imputed using the following convention:

- If the partial date is a start date, a '01' will be used for the day and 'Jan' will be used for the month.
- If the partial date is a stop date, a '28/29/30/31' will be used for the day (dependent on the month and year) and 'Dec' will be used for the month.

The recorded partial date will be displayed in listings. No imputation will be performed for completely missing start and end dates.

7.2. AE Start and End Dates

The eCRF allows for the possibility of partial dates (i.e. only month and year) to be recorded for AE start and end dates; that is the day of the month may be missing. In such a case, the following conventions will be applied for calculating the time of onset and the duration of the event:

- Missing Start Day: First of the month will be used unless this is before the start date of first study treatment; in this case the study treatment start date will be used and hence the event is considered treatment emergent.
- Missing Stop Day: Last day of the month will be used, unless this is after the stop date of study completion; in this case the study stop date will be used.

Completely missing start or end dates will remain missing, with no imputation applied. Consequently, time to onset and duration of such events will be missing.

Statistical Analysis Plan

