7.5.3. Reporting Procedures and Requirements

7.5.3.1. Adverse Events

Events occurring from the time of signed informed consent will be considered as AEs. A baseline AE assessment will occur after Screening. All AEs between screening to the follow-up visit will be recorded in source and eCRF, whether or not considered study medication related. All AEs that are possibly or probably related to study medication will be followed until resolution or database lock, whichever occurs first. Also, the sign, symptom, or disease present before the baseline AE assessment are only considered AEs if they worsen after this point. Any AEs already documented at a previous assessment and designated as ongoing should be reviewed at subsequent visits as necessary. If these have resolved, this should be documented. Changes in intensity or frequency of AEs should be recorded as separate events (i.e., a new record started). The Investigator should report all AEs on the AE page(s) of the eCRF and source documents, regardless of seriousness, severity, and causality. Whenever possible, an AE will be reported using a diagnostic term, (e.g., "common cold" or "upper respiratory infection" rather than "runny nose, cough, mild fever") and should be described with the attributes described in [Section 7.5.1.1](#).

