5. ANALYSIS PERIODS

There will be two treatment periods within Part A. Analysis phases and treatment periods:

- SCREENING analysis phase starts with sign of Informed Consent and ends with first IMP administration;
- TREATMENT PERIOD 1 analysis phase/period starts with first IMP administration within Part A and ends with second IMP administration within Part A;
- TREATMENT PERIOD 2 analysis phase/period starts with second IMP administration within Part A and ends with the end of study.

There will be one treatment period within Part B. Analysis phases and treatment periods:

- SCREENING analysis phase starts with sign of Informed Consent and ends with first IMP administration;
- TREATMENT PERIOD analysis phase/period starts first study drug administration and ends with the end of study.

Statistical Analysis Plan

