6.6.1. Adverse Events (AE)

All verbatim AE terms will be coded using MedDRA of latest version (version will be clarified in the output footnotes) and summarized by system organ class (SOC) and preferred term (PT).

A TEAE will be defined as any AE that has an onset on or after taking study drug, or any pre-existing condition that has worsened on or after taking study drug. For Part A each TEAE will be attributed to treatment period and treatment according to onset date.

The frequency and incidence of TEAEs will be summarised by SOC and PT by treatment according to treatment period and overall. Summaries will also include, but not limited to, relationship to study drug and maximum severity. The summary will be sorted by SOC and PT by frequency from the highest to the lowest. All AE data will be listed.

For each of the summaries produced at the participant level, multiple occurrences of the same event within a participant will be counted once in the summaries by SOC and PT; multiple occurrences of the same event within a participant will be counted once in the maximum severity category and/or maximum drug relationship category. If severity or relationship is found to be missing, the most severe occurrence will be imputed for that particular summary.

These summaries will also present the number of events that occurred, so multiple occurrences of the same event within a participant will all be accounted for in the maximum intensity category and maximum relationship category they were classed as.

6.6.2. 12-lead electrocardiogram (ECG)

Descriptive statistics will be calculated for absolute value and change from baseline (pre-dose) of each parameter by visit and by treatment according to treatment period and overall. Where multiple values are recorded at a timepoint for a subject, the mean of the values will be used in the summary statistics.

Statistical Analysis Plan

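### The SAP rule for AEs with a missing start day makes known pre-dose events treatment-emergent and, in Part A, credits most such Period 2 events to the Period 1 treatment

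*SAP*

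**What the plan says.** SAP 7.2 (AE Start and End Dates) covers records with a known month and year but no day: "The eCRF allows for the possibility of partial dates (i.e. only month and year) to be recorded for AE start and end dates". For a missing start day the rule has two steps. The default is "First of the month will be used unless this is before the start date of first study treatment". The exception is "in this case the study treatment start date will be used and hence the event is considered treatment emergent".

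Three other places determine what the imputed date does:

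- SAP 6.6.1 on treatment emergence: "A TEAE will be defined as any AE that has an onset on or after taking study drug". Worsening of a pre-existing condition after dosing also counts.
- SAP 6.6.1 on the crossover: "For Part A each TEAE will be attributed to treatment period and treatment according to onset date".
- SAP 5 on the Part A windows. Period 1 "starts with first IMP administration within Part A and ends with second IMP administration within Part A". Period 2 "starts with second IMP administration within Part A and ends with the end of study".

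Pre-dose events enter the database. Protocol 7.5.3.1 counts AEs from signed consent and states "All AEs between screening to the follow-up visit will be recorded in source and eCRF". Screening may be up to 28 days before dosing. In Part B the pre-dose period also contains two capsaicin injections, at the additional screening visit and on Day -1.

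**The concern.** Treating an AE as treatment-emergent when its onset cannot be placed before or after dosing is a sensible cautious convention. The exception in SAP 7.2 goes further. It also catches events whose recorded month already places them before dosing, so it conflicts with the SAP's own definition of a TEAE. An event that had also stopped before dosing would get a start date later than its stop date, in a section meant to support onset and duration calculations.

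In Part A the period determines the drug. A rule tied to the first dose, followed by attribution on onset date alone, can charge an event that began after the second dose to the other treatment. Safety and tolerability of KLS-GABA against KLS is the Part A secondary objective, with 12 subjects planned.

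**Working it through.** **The rule in symbols.** Let F be the first day of the recorded month, D1 the first-dose date and D2 the second-dose date in Part A. SAP 7.2 gives imputed onset = the later of F and D1.

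**Consequence 1: treatment emergence.** The later of F and D1 is never before D1, so every AE with a missing start day is classed as treatment-emergent, whatever month was recorded.

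**Consequence 2: Part A attribution.** By SAP 5 and 6.6.1 the event goes to Period 1 if the imputed onset is before D2. Because D1 is always before D2, this happens exactly when F is before D2:

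- Recorded month earlier than D2's month: Period 1, correctly with respect to D2.
- Recorded month equal to D2's month: Period 1, unless D2 is the 1st. This is wrong for any event that began after D2.
- Recorded month later than D2's month: Period 2, correctly.

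**Worked dates.**

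| D1 | D2 | True onset | Recorded | Imputed | Result |
|---|---|---|---|---|---|
| 5 Aug | 14 Aug | 20 Jul | Jul | 5 Aug | TEAE; wrong |
| 5 Aug | 14 Aug | 15 Aug | Aug | 5 Aug | Period 1; wrong, through the move to D1 |
| 26 Aug | 4 Sep | 5 Sep | Sep | 1 Sep | Period 1; wrong, through the first-of-month step |
| 20 Aug | 29 Aug | 2 Sep | Sep | 1 Sep | Period 2; correct |
| 23 Aug | 1 Sep | 3 Sep | Sep | 1 Sep | Period 2; correct |

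**How often the calendar produces this, given a missing day.** The plan states no figure to reproduce. Assume dosing dates uniform over the 365 days of an illustrative year (2021).

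*Pre-dose onsets, 1 to 28 days before D1.* There are 365 × 28 = 10,220 combinations. For dosing on day d of a month (d up to 28), 29 − d of the 28 onset days fall in an earlier month, so each month contributes 28 × 29 / 2 = 406. The share is 12 × 406 / 10,220 = 4,872 / 10,220 = 47.7%. By lead time, k / 30.4 gives 23% at 7 days, 46% at 14 days and 92% at 28 days, but only 3% for the day before dosing.

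*Period 2 onsets, 0 to w days after D2.* Attribution is correct if D2 is the 1st (w + 1 onset days per month) or if onset spills into the next month (w(w + 1)/2 per month).

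- w = 2: 12 × (3 + 3) = 72 of 1,095 correct, so 93.4% wrong.
- w = 5: 12 × (6 + 15) = 252 of 2,190 correct, so 88.5% wrong.
- w = 7: 12 × (8 + 28) = 432 of 2,920 correct, so 85.2% wrong.

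These totals do not depend on the gap between doses; only the split between the two mechanisms does. For assumed gaps of 7 to 14 days, the first-of-month step accounts for 7 × 12 / 365 = 23% to 14 × 12 / 365 = 46% of all Period 2 onset days. The move to D1 accounts for the remaining 39% to 70%, depending on gap and window. Cases with D1 itself on the 1st, where both steps give the same date, are counted under the first-of-month step.

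**Effect of one event.** With 12 subjects, one reassigned subject changes a treatment's incidence by at most 1/12 = 8.3 percentage points in a given row.

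**The case against.** The strongest reply is that the rule will rarely fire. Part A subjects are resident from Day -1 to 48 hours after each dose, and Part B subjects from Day -1 to 12 hours, with scheduled AE checks throughout. Follow-up comes 5 to 7 days after the last dose, so recall is short. Protocol 11.1 has missing or inconsistent eCRF entries queried and resolved before database lock. This stands: the percentages above are conditional on a missing day, and the documents give no basis for estimating how many there will be.

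Other points also stand in part:

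- Protocol 7.5.3.1 says conditions present before the baseline AE assessment count only if they worsen later. This narrows the pre-dose window but does not close it.
- Both pre-dose capsaicin injections are given at visits with AE monitoring, so their effects should usually be fully dated, and a Day -1 event seldom falls in an earlier month.
- An 8.3-point shift requires that the subject has no other event in the same row, since SAP 6.6.1 counts subjects once per SOC and PT.
- SAP 3 rules out hypothesis testing, and all AE data are listed.

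A reader might infer that all Part A Period 2 events go to the wrong drug, or that the move to the dosing date is the only cause. Neither follows. Fully dated events are unaffected, later-month events and second doses on the 1st are handled correctly, and when the doses fall in different months the cause is the ordinary first-of-month step. Nor do the documents support a bias against one product. Part B arms and Part A sequences are randomised, so false TEAEs should balance across arms in expectation, and misattributed Part A events tend to blur the contrast between treatments.

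None of this rescues the rule in the cases where it does apply. No other passage adds a same-month condition or a Period 2 rule.

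**Conclusion.** The concern holds as a drafting defect with two parts. First, a day-missing AE from a month before the dosing month is made treatment-emergent against the SAP's own definition. Second, in Part A a day-missing event that began after the second dose, in that dose's month, is credited to the Period 1 treatment unless the second dose was on the 1st.

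Both follow from the text alone. The calendar shares (47.7% of pre-dose onset days; 85% to 93% of Period 2 onset days) rest on assumed uniform dosing dates and the stated windows, and apply only to events with a missing day. With few such events likely and a descriptive safety analysis, the practical effect is probably small. It is a minor correction, worth making because it is cheap and concerns which drug an event is counted under.

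**What to change.** Amend SAP 7.2 as follows.

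- Impute the dosing date only when the recorded month and year equal those of the dose and any known stop date is not before that dose.
- Classify an event whose recorded month precedes the dosing month as not treatment-emergent, unless it worsened after dosing. Protocol 7.5.3.1 already asks for a new record when intensity or frequency changes, so worsening should have its own start date.
- In Part A, apply the rule against the dose of the period in which the event was reported. For an event reported after the second dose and recorded in that dose's month, this replaces both the first-of-month step and the move to the first dose.
- If the reporting period cannot be determined, use one prespecified convention and flag the event in the listings. Assigning it to the most recent treatment or counting it under both are possible choices; counting under both raises both incidences.

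The cost is a few sentences and the matching derivation code. No new data should be needed, assuming the eCRF shows the visit at which each AE was reported; Protocol Appendix 1 schedules AE monitoring within each period.
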